8.2.1.2. Ganciclovir Pharmacokinetics/Adherence

Assessment of ganciclovir plasma concentrations will be conducted at the UAB Central Pharmacokinetic Laboratory. Ganciclovir concentrations will be obtained with one of the Study Assessment Doses 3, 4, 5, 6, 7, or 8 (Window: Study Assessment Day 1 through Study Assessment Day 5). Timepoints for

pharmacokinetic draws are as follows: 0h (immediately prior to IV ganciclovir dose; window: -15 min), 1h (immediately after the end of the IV ganciclovir dose; window: +15 min), 2-3h, 5-7h, and 10-12h. The required amount of whole blood for plasma ganciclovir determination at each timepoint is 200 μ L (0.2 mL). Specimens will be processed to separate the plasma, which will be shipped to the UAB Central Pharmacokinetic Laboratory.

If desired by the treating physicians and the subject weighs \geq 575 grams at that time, ganciclovir concentrations may be evaluated again around one dose in this assessment window (Study Assessment Day 18 through Study Assessment Day 24). Timepoints for pharmacokinetic draws are as follows: 0h (immediately prior to IV ganciclovir dose; window: -15 min), 1h (immediately after the end of the IV ganciclovir dose; window: +15 min), 2-3h, 5-7h, and 10-12h. The required amount of whole blood for plasma ganciclovir determination at each timepoint is 200 μ L (0.2 mL). Specimens will be processed to separate the plasma, which will be shipped to the UAB Central Pharmacokinetic Laboratory. If subject weighs $<$ 575 grams, the second set of PK draws cannot be performed.

A rapid, sensitive and specific high performance liquid chromatographic (HPLC) assay is used for the determination of ganciclovir in 200uL of human plasma. The UV detector, set to monitor the 270nm wavelength, provides adequate sensitivity with minimal interference from endogenous matrix components. The calibration curves are linear for ganciclovir over the range of 10 to 10,000 ng/mL.

8.2.2 Specimen Preparation, Handling, and Shipping

8.2.2.1 Instructions for Specimen Preparation, Handling, and Storage

Specific instructions on specimen preparation, handling and storage will be provided in the Manual of Procedures for this study.

8.2.2.2 Specimen Shipment

Specific instructions on specimen shipping will be provided in the Manual of Procedures for this study.

8.3 PRBC Transfusion Assessment

PRBC transfusions are commonly required in the management of critically ill premature babies. Because of the fragile nature of these subjects and the concern of risk of increasing the frequency of blood transfusions in participants in this sampling study, once during each Study Period the study team will record the number of PRBC transfusions received by the study subject since enrollment (for the Period 1 documentation) or since the last recording (for documentation for Periods 2-7). A PRBC transfusion is defined as ≥ 10 mL/kg of PRBCs within a 24 hour period.

9 ASSESSMENT OF SAFETY

This is a non-interventional sampling study. Risk to subjects is limited to risks associated with blood draws. In an effort to document only untoward medical events that have a greater likelihood of being study-related, only adverse events associated with blood draws will be considered adverse events for the purposes of this protocol. These events will be reported as adverse events of special interest (AESIs). Information to be collected includes event description, time of onset, clinician's assessment of severity, relationship to blood draw (assessed only by those with the training and authority to make a diagnosis, which would include MD or DO), and time of resolution/stabilization of the event. AEs will be followed to adequate resolution.

Any other adverse events that meet the reporting requirements of the Institutional Review Board will be documented as AESIs, and reported to Protocol Chair, DMID Medical Officer, Medical Monitor and the Clinical Project Manager.

9.1 Safety Reporting: Adverse Events of Special Interest (AESI)

The investigator must also report the following AESI on the AESI case report form:

- AEs associated with blood draws
- All adverse events that meet the reporting requirements of the Institutional Review Board (which will also be reported to Protocol Chair, DMID Medical Officer, Medical Monitor and the Clinical Project Manager).

○

9.2 Type and Duration of Follow-up of Subjects after Adverse Events

All AEs as described above will be followed until resolved or considered stable.

9.3 Halting Rules

9.3.1 Discontinue of Study participation for individual subject.

Subjects who experience significant problems with blood draws may be withdrawn from any future sampling. Transfusions are expected in hospitalized premature infants. One study reported that extremely premature neonates receive an average of 5.2 ± 4.2 transfusions over a six week period.³¹ Other trials have reported similar numbers of transfusions in this population.^{32,33} It is possible that even higher numbers of transfusions might be experienced in

the at-risk population in this sampling study since they are receiving the myelosuppressive drug ganciclovir as part of clinical care. Transfusions are not associated with long-term sequelae.³³ Nevertheless, if a study subject receives ≥ 10 PRBC transfusions during the course of the study, all future study-related blood draws will not be performed.

9.3.2 Discontinuation of Study Enrollment Pending Sponsor Review

DMID may interrupt study testing and/or study entry at any time if medically indicated. To minimize risk, the Protocol Chair, DMID Medical Officer, and Medical Monitor will review cumulative safety data.

Study enrollment and dosing will be stopped, and an ad hoc review will be performed if:

- X of the first Y subjects enrolled have more than 5 packed red blood cell (PRBC) transfusions during their period of time on the study, according to the table below. For a PRBC transfusion to be counted toward this halting rule, it must involve ≥ 10 mL/kg of PRBCs administered within a 24 hour period of time.

Number enrolled (Y)	Stop/Investigate when number with events equals this number (X)	type I error	power when mean=7
4	4	0.0218	0.2391
5	5	0.0084	0.1672
6	5	0.0341	0.4186
7	6	0.0151	0.3279
8	6	0.0406	0.5500
9	7	0.0196	0.4609
10	7	0.0438	0.6477
11	8	0.0225	0.5675
12	8	0.0450	0.7218
13	9	0.0242	0.6522
14	9	0.0450	0.7787
15	10	0.0251	0.7195
16	10	0.0442	0.8230
17	11	0.0254	0.7732
18	11	0.0429	0.8578
19	12	0.0253	0.8162
20	12	0.0414	0.8853

21	13	0.0248	0.8506
22	13	0.0397	0.9072
23	14	0.0242	0.8784
24	14	0.0378	0.9246
25	15	0.0234	0.9008
26	15	0.0360	0.9387
27	16	0.0226	0.9189
28	16	0.0342	0.9500
29	16	0.0496	0.9701
30	17	0.0324	0.9592
31	17	0.0465	0.9756
32	18	0.0307	0.9666

This halting rule is supported by an NICHD study that reported that extremely premature neonates receive 5.2 ± 4.2 transfusions per patient.³¹ Other trials have reported similar numbers of transfusions in this population.^{32,33} We therefore will anticipate up to 5 transfusions of PRBCs per subject. Subjects who would qualify for study enrollment are very sick, and frequent PRBC transfusions may be related to their underlying illness and not to the study-related blood draws. If following the review additional study enrollment is deemed safe, enrollment may be allowed to resume. Assuming the number of transfusions follows a Poisson distribution with mean of 5, then the probability of a subject receiving more than 5 PRBC transfusions is 0.384 (or 38.4%). If the halting rule is to stop the study when exactly 4 subjects receive more than 5 transfusions, then the probability of halting the study based on the given assumptions is 0.001 (or 0.1%) using a Binomial distribution with n=32 and probability of success equal to 0.384.

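### The halting table's power at mean 7 assumes Poisson counts, but the spread the protocol cites (5.2 ± 4.2) is far wider, and power at 32 subjects falls from 0.967 to about 0.36–0.67.

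*Protocol*

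**What the plan says.** Protocol section 9.3.2 stops enrollment for an ad hoc review when "X of the first Y subjects enrolled have more than 5 packed red blood cell (PRBC) transfusions", with the pairs X and Y listed from 4 of 4 up to 18 of 32. Each row carries a type I error and a column headed "power when mean=7". At 32 subjects these are 0.0307 and 0.9666.

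The rule is justified by a study in which "extremely premature neonates receive 5.2 ± 4.2 transfusions per patient". Section 9.3.1 gives the time base of the same figures: infants "receive an average of 5.2 ± 4.2 transfusions over a six week period".

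The calculation then proceeds "Assuming the number of transfusions follows a Poisson distribution with mean of 5", from which the protocol takes 0.384 as the chance that an infant exceeds 5 transfusions. The table does not name the distribution behind its power column. Neither document offers an overdispersed alternative or a sensitivity analysis, and the data analysis plan in SAP Appendix B does not cover the halting rule.

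**The concern.** The assumption and its supporting evidence, given in the same section, do not agree. A Poisson count with mean 5 has a standard deviation of 2.24; the cited standard deviation is 4.2.

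The mismatch is easy to miss because the cut at 5 lies near the null mean. There, extra spread hardly changes the proportion of infants above the cut, so the type I column looks sound. The effect appears at the alternative: when counts are widely spread, raising the mean to 7 moves far fewer infants past 5 than a Poisson model predicts.

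This is the only study-level stopping boundary in the plan, and blood loss from sampling is the main risk the protocol names. Someone who believes the rule has about 97% power at 32 subjects would take an uncrossed boundary as strong evidence that transfusions have not risen. On the protocol's own cited spread, that reassurance is not earned.

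**Working it through.** **Inputs.** Null mean 5, alternative mean 7, the event of more than 5 transfusions, and the pairs (Y, X), all from section 9.3.2. Mean 5.2 and SD 4.2 from section 9.3.2, over six weeks from section 9.3.1. The ± 4.2 is read as a between-patient SD.

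**Step 1: reproduce the table.**
- p0 = P(Poisson(5) > 5) = 0.3840
- p1 = P(Poisson(7) > 5) = 0.6993
- Type I error = P(Binomial(Y, p0) ≥ X); power = P(Binomial(Y, p1) ≥ X)

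These match all 29 rows of both columns to four decimals. At Y = 32, X = 18 they give 0.0307 and 0.9666. So the power column is Poisson(7), although the table does not say so.

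**Step 2: the cited spread.**
- Variance = 4.2² = 17.64
- Variance/mean = 17.64 / 5.2 = 3.39 (Poisson requires 1)
- Negative binomial by moments, with variance = mean + mean²/k: k = 5.2² / (17.64 − 5.2) = 27.04 / 12.44 = 2.17

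**Step 3: type I error with that spread.** With k = 2.17, P(>5) is 0.363 at mean 5 and 0.381 at mean 5.2, against 0.384. At Y = 32, X = 18 the type I error is 0.017 or 0.028, against 0.0307. With the null at 5.2, the largest value in any row is 0.0464 (Y = 29, stated 0.0496). No row is inflated.

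**Step 4: power at mean 7.** The documents do not say how the SD changes when the mean rises, so four ways of carrying it forward are shown. For a given SD at mean 7, k = 49 / (SD² − 7).

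| Carried to mean 7 | SD | k | P(>5) | Power, Y=16, X=10 | Power, Y=32, X=18 | Ever crossing by Y=32 |
|---|---|---|---|---|---|---|
| Poisson (as tabulated) | 2.65 | – | 0.699 | 0.823 | 0.967 | 0.986 |
| Constant CV | 5.65 | 1.96 | 0.515 | 0.27 | 0.36 | 0.57 |
| Constant k | 5.44 | 2.17 | 0.524 | 0.29 | 0.40 | 0.60 |
| Constant variance/mean | 4.87 | 2.93 | 0.550 | 0.37 | 0.52 | 0.70 |
| SD fixed at 4.2 | 4.20 | 4.61 | 0.585 | 0.48 | 0.67 | 0.81 |

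The last column is not in the protocol. It was obtained by exact recursion, applying the boundary after each subject from Y = 4 to 32.

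**Step 5: does the direction depend on the negative binomial?** Every row of the table loses power under all four variants. A crude normal(7, 4.2) with a cut at 5.5 fits poorly because it allows negative counts; it gives 0.86 at Y = 32, still below 0.967.

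**The case against.** **The table is correct under a declared model.** This stands. The Poisson assumption is stated and every entry follows from it. A reader might infer a calculation error; there is none. What fails is the support for the assumption.

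**The size rests on assumptions outside the documents.** This also stands. Neither the negative binomial form nor the scaling of the SD is given. The figures above also hold the boundaries fixed. If the null mean stays at 5 with k = 2.17 and the boundaries are re-derived at the same 0.05 limit, nine of the 29 fall by one. At Y = 32 that means X = 17, with power of 0.50 to 0.79. The shortfall narrows but remains.

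**Exposure may matter more than dispersion.** The cited figures cover six weeks. The schedule of events captures data after Period 1 only while ganciclovir continues, and the background section puts typical treatment at two to four weeks. If counts scale with time (an assumption), four weeks at a rate of 7 per six weeks has mean 7 × 4/6 = 4.67. Power at Y = 32, X = 18 is then below 0.01 under Poisson and negative binomial alike. So recomputed figures would not be the true power for shorter stays. This is a reason to state the exposure assumption, not to leave the Poisson column standing.

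**Other safeguards exist.** This stands too. A reader might take the table as the trial's only quantitative protection. But section 9.3.1 ends study blood draws for an infant with 10 or more transfusions, the schedule of events caps study blood at 7 mL/kg over 42 days, and the SAP requires a monthly report of transfusion numbers. Section 9.3.2 also provides for review of cumulative safety data, and crossing the boundary triggers a review after which enrollment may resume. These limit the consequences of low power; they do not make the stated power right.

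**Type I error.** A reader might infer that it too is understated, since a Poisson mean of 5.2 in place of 5 gives 0.072 at Y = 32 against 0.0307. That pairs the cited mean with the very distribution that the cited SD rules out. Under a distribution matching both figures, no row is inflated.

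**Conclusion.** The concern holds for the power column only. The table is arithmetically right under Poisson means of 5 and 7, but the source cited for the rule has a variance 3.4 times its mean. With a negative binomial matching that source, type I error stays at or below the stated values, while power at mean 7 falls well short: 0.36 to 0.67 rather than 0.9666 at 32 subjects, 0.27 to 0.48 rather than 0.8230 at 16, and 0.57 to 0.81 rather than 0.986 for ever crossing.

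The exact size depends on the negative binomial form, on how the spread scales to mean 7, on reading ± 4.2 as a between-patient SD, and on full six-week exposure. The direction was the same in every variant tried. The documents do not support the wider inferences that false stopping is more likely than stated, or that excess transfusions would go unobserved.

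**What to change.** In Protocol section 9.3.2:

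- Recompute the type I and power columns with an overdispersed distribution, such as a negative binomial, consistent with 5.2 ± 4.2.
- Name the distribution used for each column.
- Give the power at mean 7 as a range over the ways the dispersion may carry to the higher mean, rather than as one figure to four decimals.
- State that the figures assume six weeks of observation per infant, and that shorter time on study lowers them.

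No further monitoring summary is needed for this point, since the SAP already schedules a monthly transfusion report. Whether the restated power is acceptable for the existing boundary is for the sponsor to decide.

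The cost is a recalculation and one replaced table. No new data are required. The stated power becomes less favourable.

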2 BACKGROUND INFORMATION AND SCIENTIFIC RATIONALE

2.1 Background Information

The natural history of congenitally acquired CMV infection is well described.¹⁻⁷ In contrast, outcomes of perinatally and postnatally acquired CMV infections are less well characterized. It is generally agreed that postnatal acquisition of CMV in term infants does not lead to symptomatology or disease.⁸ In preterm infants, initial case reports suggested that peri- and postnatally acquired CMV infections could produce severe disease.⁹⁻¹⁴ Larger series and case-controlled trials more recently suggest that symptomatic disease in preterm babies is less common than asymptomatic infection, and long-term sequelae are rare.¹⁵⁻¹⁹ Nevertheless, severe disseminated CMV disease can occur in premature infants, including life-threatening pneumonitis, hepatitis, and thrombocytopenia.²⁰ Antiviral therapy in such patients is frequently used, albeit without either controlled data to demonstrate benefit or knowledge of proper dosing regimens.¹² In patients with symptomatic congenital CMV disease, six weeks of intravenous ganciclovir improves hearing outcomes in early childhood,²¹ and may benefit neurodevelopmental outcomes as well.²² In premature babies with visceral disease from postnatally acquired CMV, the goal of antiviral therapy is different; namely, it is to treat the end-organ disease, which is occurring at that time, rather than to prevent or improve long-term sequelae. Without efficacy data, the duration of treatment is variable, but anecdotal experience suggests that it generally is in the range of two to four weeks of total antiviral therapy. Approximately two-thirds of treated neonates receiving six weeks of intravenous ganciclovir develop Grade 3 or 4 neutropenia (utilizing the DAIDS Toxicity Tables) during therapy.²¹

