Ganciclovir pharmacokinetics		X ^h		X ^{i,j}			
Virology blood specimens for CMV viral load ^k	X ^l	X ^l	X ^l	X ^l	X ^l	X ^{l,m}	X ^{l,n}
CMV detection from noninvasive urine specimen	X ^o	X ^o	X ^o	X ^o	X ^o	X ^o	X ^o
Ganciclovir dosing information	X ^p	X ^p	X ^p	X ^p	X ^p	X ^p	X ^p
PRBC transfusion assessment	X ^q	X ^q	X ^q	X ^q	X ^q	X ^q	X ^q

Assessment for AEs or SAEs		X	X	X	X	X	X
Total volume of blood required for study procedures	1.75 mL	0.5 mL	0.5 mL	0.5 mL or 1.5 mL ⁱ	0.5 mL	0.5 mL	0.5 mL

a) Data and specimens in this column to be captured if subject still receiving ganciclovir as clinical treatment

b) Gestational age at delivery, date of birth, day of life at initiation of IV ganciclovir therapy, gender, race, ethnicity, birth weight, weight at enrollment, length in centimeters at enrollment, reason ganciclovir being administered, ganciclovir dose and dosing frequency, manufacturer of the ganciclovir lot utilized at the treating facility, date ganciclovir therapy was initiated

c) Window: Birth through Study Assessment Day 3)

d) WBC with differential, hemoglobin, platelet count. Optional laboratory draws are not required by the protocol, and so no documentation on a source document will be required.

e) If being drawn for clinical reasons; any laboratory value obtained during the window will suffice, with an effort being made to capture the most abnormal value. Optional laboratory draws are not required by the protocol, and so no documentation on a source document will be required.

f) AST, ALT. Optional laboratory draws are not required by the protocol, and so no documentation on a source document will be required.

g) To be drawn on the calendar day that ganciclovir PKs are being drawn. Study related laboratory draws will be delayed or deferred if the investigator believes that obtaining them might increase subject risk. Additionally, a study-related laboratory specimen that is unevaluable due to clotting or laboratory related issues will not be repeated. If a study related laboratory draw is delayed or deferred, study staff will document this on a source document.

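### Protocol 9.3.2: the stated 0.1% halting probability is the chance of exactly 4 events among 32, for a rule not in the table; the tabulated rule's overall chance of triggering (13.8% at mean 5, 98.6% at mean 7) is not given

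*Protocol*

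**What the plan says.** Protocol section 9.3.2 stops enrolment for an ad hoc review when X of the first Y subjects "have more than 5 packed red blood cell (PRBC) transfusions during their period of time on the study". A table gives X for every Y from 4 (X = 4) to 32 (X = 18), with a type I error and a power at mean 7 in each row. The closing text sets the null: "Assuming the number of transfusions follows a Poisson distribution with mean of 5", so that a subject exceeds 5 with probability 0.384. It next supposes a rule triggered by exactly four such subjects, and concludes that "the probability of halting the study based on the given assumptions is 0.001 (or 0.1%) using a Binomial distribution with n=32". No other probability of halting appears in the protocol or SAP.

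The benchmark comes from a cited study in which extremely premature neonates "receive an average of 5.2 ± 4.2 transfusions over a six week period" (section 9.3.1).

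On how long transfusions are counted, section 8.3 sets no condition about ganciclovir: "once during each Study Period the study team will record the number of PRBC transfusions received by the study subject since enrollment". From Period 2 on, each entry counts from the one before. Sections 7.3 and 7.4 put transfusion documentation ahead of the check that ganciclovir continues. Note (a) to the Appendix A schedule, repeated in the SAP's CRF Workflow table, applies to the whole of Periods 2 to 7: "Data and specimens in this column to be captured if subject still receiving ganciclovir as clinical treatment".

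**The concern.** Section 9.3.2 contains the only numeric trigger at enrolment level, in very fragile infants. A reader who wants to know how often it would fire finds one figure called a probability of halting, 0.1%. The figure looked wrong for two reasons. With an expected 32 × 0.384 = 12.3 subjects exceeding 5 transfusions under the null, reaching four is close to certain. And four is the table's boundary only at Y = 4.

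The rule that is in force has 29 boundaries, but only row-by-row values are printed. A reader could take the largest of these, about 5%, as the chance of a false trigger for the study, or take the 0.1% at face value. Both understate it. A committee facing a crossing would then have the wrong idea of how surprising it is.

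**Working it through.** **Inputs (section 9.3.2).** Null mean 5, alternative mean 7, Poisson; event = more than 5 transfusions; n = 32; boundaries X = 4, 5, 5, 6, 6, 7, 7, 8, 8, 9, 9, 10, 10, 11, 11, 12, 12, 13, 13, 14, 14, 15, 15, 16, 16, 16, 17, 17, 18 for Y = 4 to 32.

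**1. Event probabilities.** P(more than 5) = 1 − Σ(k = 0..5) e^(−m) m^k / k!. This gives 0.3840 at m = 5, as stated, and 0.6993 at m = 7.

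**2. The stated 0.001.** P(X = 4) = C(32,4) × 0.384⁴ × 0.616²⁸ = 35,960 × 0.021743 × 1.2831×10⁻⁶ = 0.00100. The plan's figure is reproduced, and it is a point probability.

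**3. What stopping at four events would give.** P(X ≥ 4) = 1 − [P(0) + P(1) + P(2) + P(3)] = 1 − 0.00026 = 0.9997. Reading the sentence as the table's first row (4 of the first 4) does not rescue it: 0.384⁴ = 0.0217, and the table prints 0.0218 from unrounded p. At 32 subjects the tabulated boundary is 18, with tail probability 0.0307.

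**4. The table.** All 58 entries reproduce to within 0.00005 as single-look tails P(Binomial(Y, p) ≥ X). They cannot be cumulative: power falls from 0.2391 at Y = 4 to 0.1672 at Y = 5.

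**5. Overall probability of the tabulated rule.** Carry the distribution of the event count forward one subject at a time, removing any path that reaches X at its Y. The first steps at mean 5 show the method:
- Y = 4: p⁴ = 0.0218.
- Y = 5: nothing new, because 5 of 5 implies 4 of 4.
- Y = 6: five events with the single non-event among the first four adds 4 × p⁵ × (1 − p) = 4 × 0.00835 × 0.6160 = 0.0206, so the total is 0.0423.

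Continuing at mean 5 gives 0.0594 by Y = 8, 0.1013 by Y = 16, 0.1215 by Y = 24 and **0.1385** (0.1384996) by Y = 32. At mean 7 the result is **0.9855**. Simulation of 400,000 trials gives 0.1385 and 0.9857.

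**6. Sensitivity to spread.** A Poisson with mean 5 has SD 2.2; the cited figure is 5.2 ± 4.2. Overall crossing probability:

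| Per-subject counts | P(more than 5) | Overall |
|---|---|---|
| Poisson, mean 5 | 0.384 | 13.8% |
| Negative binomial, 5.2 ± 4.2 (as cited) | 0.381 | 13.3% |
| Negative binomial, 5 ± 4.2 | 0.360 | 9.6% |
| Poisson, mean 5.2 | 0.419 | 22.3% |

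The cited pair lands near 13.8% because its higher mean and wider spread offset each other. At mean 7 the dispersion has to be assumed. Overall power is 57% (size parameter from 5 ± 4.2), 60% (size from 5.2 ± 4.2), 70% (same variance-to-mean ratio as 5.2 ± 4.2) or 81% (SD held at 4.2).

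**7. Counting period, illustration only.** Assume a constant Poisson rate and four weeks for every infant. Six-week means of 5 and 7 become 5 × 4/6 = 3.33 and 7 × 4/6 = 4.67, with P(more than 5) = 0.121 and 0.326. The overall crossing probabilities become 0.04% and 5.4%.

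**The case against.** The strongest reply is that the faulty sentence is inert. It is conditional, sets no boundary, and sits beneath a table that is arithmetically right. The protocol claims no overall error control, so a missing 29-look probability is an omission rather than an error. A crossing opens a review, after which enrolment may resume. Other safeguards exist: study draws stop for a subject at 10 or more transfusions (9.3.1), the sponsor may interrupt entry at any time (9.3.2), data are reviewed after the first four subjects (15.4), and transfusions are reported monthly (SAP, Creating Reports). All of this stands and limits the consequence. It does not make 0.1% a probability of halting.

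A reader might go further and infer that the rule would almost never fire, because section 2.1 says of treatment duration that "it generally is in the range of two to four weeks of total antiviral therapy". The documents do not support that:
- The statement is described as anecdotal, concerns postnatally acquired visceral disease, and refers to total therapy rather than time after enrolment. The study also covers congenital infection, for which section 2.1 describes six-week courses.
- Section 9.3.2 sets its means per subject over time on study. Treating 7 as a six-week rate is a rescaling that the protocol does not make.
- The four-week figures are fragile. With negative binomial counts using the dispersion from 5.2 ± 4.2, the 0.04% becomes about 0.3%.

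Nor do the SAP's rules on form access (Appendix C, 4.3.8.5 and 4.3.10) clearly contradict each other. They can be read as two workflows, one for a subject who has not completed the last dose and one for after the last dose.

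**Conclusion.** Wrong as written, with limited consequence. The stated 0.1% is P(exactly 4 of 32). Stopping at the fourth event would have probability 99.97%, and that is not the tabulated rule. The tabulated rule triggers at least one review with probability 13.8% at mean 5, nearly three times the largest listed single-look value of 4.96%, and 98.6% at mean 7. These two figures assume independent subjects, Poisson counts with those means over time on study, and complete counts at every look from 4 to 32. If counts are as dispersed as the cited study suggests, the power figure is the more sensitive of the two to that assumption.

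It would be too strong to conclude that the table is miscalculated or that its boundaries are unsafe. The entries are right for single looks, and nothing in the documents fixes an overall level that the rule fails to meet.

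A secondary point also holds. Note (a) in Appendix A conflicts with sections 7.3, 7.4 and 8.3 on whether transfusions are counted after ganciclovir stops. Because the benchmark of about 5 covers six weeks, shorter counting lowers the chance of triggering. The documents do not settle by how much.

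**What to change.** 1. Delete the sentence giving 0.001.
2. Label the type I error and power columns as per look.
3. In place of the deleted sentence, state: *If the rule is checked at every Y from 4 to 32, with independent subjects, Poisson counts over time on study and counts complete at each look, the probability of at least one triggered review is 13.8% at a per-subject mean of 5 and 98.6% at a mean of 7.*
4. Optionally, add a sensitivity line: negative binomial counts at the cited 5.2 ± 4.2 give 13.3%, and overall power at mean 7 falls to about 57–81% depending on the assumed dispersion.
5. Separately, reconcile Appendix A note (a), and its copy in the SAP, with sections 7.3, 7.4 and 8.3 on when transfusion counting ends. Section 7.5, on follow-up after therapy stops, should be checked at the same time. The figures in item 3 are conditional on the per-subject means, so they remain valid statements either way; the answer decides whether a six-week benchmark is the right source for those means.

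The cost is one sentence replaced, two column labels, at most one further line and one reconciled footnote. It needs no new data. The stated properties will look less favourable than before. No boundary change is proposed; any such change is for the sponsor to decide.
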